- 2.1.4 Cohort 2A Checkpoint Inhibitor Previously Treated Patients that Previously Achieved a Complete Response (CR) or Partial Response (PR) Specific Inclusion Criteria
- Patients must have been treated with at least one treatment of a PD-1/PD-L1 checkpoint inhibitor for advance or metastatic UC and achieved a complete response or partial response by RECIST 1.1 criteria.
- 2.1.5 Cohort 2B Checkpoint inhibitor previously treated patients that previously had stable disease (SD) or progressive disease (PD)
- 2.1.6 Specific Inclusion Criteria
- Patients must have been treated with at least one treatment of a PD-1/PD-L1 checkpoint inhibitor for advance or metastatic UC and had stable disease or a progressive disease by RECIST 1.1 criteria.
- 2.1.7 Exclusion Criteria
- 2.1.7.1 History of allergic reactions attributed to compounds of similar chemical or biologic composition to M7824 investigational agents used in the study.
- 2.1.7.2 Uncontrolled intercurrent illness including, but not limited to, symptomatic congestive heart failure, unstable angina pectoris, cardiac arrhythmia, or psychiatric illness/social situations that would limit compliance with study requirements.
- 2.1.7.3 Symptomatic central nervous system metastasis.
- 2.1.7.4 Subjects unwilling to accept blood products as medically indicated
- 2.1.7.5 Pregnant women are excluded from this study because M7824 is an agent with the potential for teratogenic or abortifacient effects. Because there is an unknown but potential risk for adverse events in nursing infants secondary to treatment of the mother with M7824, breastfeeding should be discontinued if the mother is treated with these agents.
- 2.1.7.6 Patients with any active or recent history of a known or suspected autoimmune disease (with the exception of diabetes type I, vitiligo, psoriasis, or hypo- or hyperthyroid diseases not requiring immunosuppressive treatment) or recent history of a syndrome that required treatment with either systemic corticosteroids (>10 mg daily prednisone equivalent) or

immunosuppressive medications. Inhaled steroids and adrenal replacement steroid doses up to 10 mg daily prednisone equivalents are permitted in the absence of active autoimmune disease.

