#### **2.3.1 Treatment Assignment Procedures**

##### **Cohorts**

Patients will be assigned to the appropriate cohort depending on prior checkpoint inhibitor therapy and documented or reviewed radiologic responses to prior checkpoint inhibitor therapy. Whenever possible prior scans will be loaded to our PACS and reviewed for cohort 2A and 2B.

Subjects from all cohorts will be treated with a flat dose of M7824 (1200 mg) every 2 weeks (+/- 3 days for scheduling issues).

Number	Name	Description
1	Cohort 1A	Checkpoint inhibitor naïve patients who are cisplatin-ineligible
2	Cohort 1B	Checkpoint inhibitor naïve patients who are refractory post-platinum therapy
3	Cohort 2A	Checkpoint inhibitor refractory patients with prior Complete Response (CR) or Partial Response (PR) as per RECIST 1.1 as best response
4	Cohort 2B	Checkpoint inhibitor refractory patients with Stable Disease (SD) or Progressive Disease (PD) as per RECIST 1.1 as best response

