#### 3.3.1.2 Adverse Drug Reactions (ADRs) Requiring Treatment Discontinuation

**Any Grade 4 ADRs require permanent treatment discontinuation** except for single laboratory values out of normal range that do not have any clinical correlate, and resolve to Grade  $\leq 1$  or baseline grade within 7 days with adequate medical management. Grade 3 or 4 symptomatic endocrinopathies (e.g., thyroiditis or hypophysitis), treatment should be delayed and treatment started according to NCCN guidelines. If condition improves to Grade 1, treatment may be resumed.

Subjects with grade 4 amylase or lipase abnormalities must permanently discontinue treatment. If the participant develops any evidence of pancreatitis, it should be managed accordingly.

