**Table 2: Management of immune- mediated adverse events**

Immune-related AEs are specific to immunotherapies and vary by organ system. The following immune-related AEs are important identified risks for M7824:
 
 
• Immune-related pneumonitis
 
• Immune-related hepatitis
 
• Immune-related colitis
 
• Immune-related nephritis and renal dysfunction
 
• Immune-related endocrinopathies
 
• (thyroid disorders, adrenal insufficiency, type 1 diabetes mellitus, pituitary disorders)
 
• Immune related rash
 
• Other immune-related events (myositis, myocarditis, encephalitis)
 
 
The following immune-related AEs are important potential risks for M7824:
 
 
• Guillain-Barré syndrome
 
• Uveitis
 
• Pancreatitis
 
• Myasthenia gravis/myasthenic syndrome
 
 
Recommended guidance and management for specific irAEs are provided in the current National Comprehensive Cancer Network (NCCN) guideline available at http://www.nccn.org.
 
Requirements in addition to NCCN guidelines:
 
 
• Permanent treatment discontinuation is required in case of immune-related Grade 4 rash/inflammatory dermatitis, nephritis, autoimmune hemolytic anemia, hemolytic uremic
 

--

syndrome, aplastic anemia, immune thrombocytopenia, acquired thrombotic thrombocytopenic purpura inflammatory arthritis, myositis and polymyalgia-like syndrome.

- For Grade 4 immune-related lymphopenia, permanent treatment discontinuation will be required, if lymphopenia is considered immune-related in nature, no clear alternative explanation exists for the event, and it does not resolve within 14 days. Permanent treatment discontinuation is not required when the AE is manifested by a single laboratory value out of normal range without any clinical correlates. In this case, treatment should be held until the etiology is determined. If the event is not considered immune-related and resolves to Grade  $\leq 1$ , restarting treatment may be considered.
- For Grade 1 immune-related pneumonitis: continue treatment. If clinically indicated, monitor participants weekly or more frequently as needed with history, physical examination and pulse oximetry. If symptoms appear and/or changes in the physical exam are noted, treat as Grade 2.

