### 3.3.1.8 Immune-Related Adverse Events

Immune-related adverse events (irAEs) are specific to immunotherapy. IrAEs are important identified risks for M7824. Immune-related adverse events should be documented as an ‘Adverse Event of Special Interest (AESI),’ and it is recommended to involve the principal investigator at first incidence and subsequently as needed for follow-up. Details of the diagnostic work-up will be requested by the study team. An immune related adverse event (irAE) is defined as off target side effects associated with exposure of immunogenic drug and is consistent with immune mechanism. In the process of identification of irAEs, any possible etiology of neoplastic, infectious, metabolic, toxin, or any other factor should be ruled out. Serologic, histologic (biopsy),

and/or immunologic results should be obtained to evaluate the differential diagnosis and/or support an immune-mediated cause.

The recommendations for irAE management, in accordance with the joint American Society of Clinical Oncology (ASCO) Clinical Practice Guidelines ([Brahmer, 2018](#)) and National Comprehensive Cancer Network ([NCCN Guidelines®](#)). General management by CTCAE v5.0 grading, as per ASCO, is listed below (ASCO organ/system specific toxicity management takes precedent over below general guidelines):

Grade 1: study treatment should be continued with close monitoring, with the exception of some neurologic, hematologic, and cardiac toxicities.

Grade 2: study treatment may be suspended for most Grade 2 toxicities, with consideration of resuming when symptoms revert to Grade 1 or less. Corticosteroids may be administered (initial dose of 0.5 to 1 mg/kg/d of prednisone or equivalent).

Grade 3: study treatment is generally suspended and the high-dose corticosteroids (prednisone 1 to 2 mg/kg/d or methylprednisolone 1 to 2 mg/kg/d) treatment should initiated. Corticosteroids should be tapered over the course of at least 4 to 6 weeks. Some refractory cases may require infliximab or other immunosuppressive therapy.

Grade 4: in general, permanent discontinuation of study treatment is recommended, with the exception of endocrinopathies that have been controlled by hormone replacement.

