## 16.2.3 Table A3 Management of Lung irAEs in Patients Treated With ICPi

3.0 Lung Toxicities	
3.1 Pneumonitis	

Definition: Focal or diffuse inflammation of the lung parenchyma (typically identified on CT imaging)            No symptomatic, pathologic, or radiographic features are pathognomonic for pneumonitis            Diagnostic work-up            Should include the following: CXR, CT, pulse oximetry            For G2 or higher, may include the following infectious work-up: nasal swab, sputum culture and sensitivity, blood culture and sensitivity, urine culture and sensitivity
	
Grading	Management
G1: Asymptomatic, confined to one lobe of the lung or < 25% of lung parenchyma, clinical or diagnostic observations only	
Hold ICPi with radiographic evidence of pneumonitis progression            May offer one repeat CT in 3-4 weeks; in patients who have had baseline testing, may offer a repeat spirometry/DLCO in 3-4 weeks            May resume ICPi with radiographic evidence of improvement or resolution. If no improvement, should treat as G2            Monitor patients weekly with history and physical examination and pulse oximetry; may also offer CXR

G2: Symptomatic, involves more than one lobe of the lung or 25%-50% of lung parenchyma, medical intervention indicated, limiting instrumental ADL	
Hold ICPi until resolution to G1 or less            Prednisone 1-2 mg/kg/d and taper by 5-10 mg/wk over 4-6 weeks Consider bronchoscopy with BAL            Consider empirical antibiotics            Monitor every 3 days with history and physical examination and pulse oximetry, consider CXR; no clinical improvement after 48-72 hours of prednisone, treat as G3

G3: Severe symptoms, hospitalization required, involves all lung lobes or 50% of lung parenchyma, limiting self-care ADL, oxygen indicated G4: Life-threatening respiratory compromise, urgent intervention indicated (intubation)	
Permanently discontinue ICPi            Empirical antibiotics; (methyl)prednisolone IV 1-2 mg/kg/d; no improvement after 48 hours, may add infliximab 5 mg/kg or mycophenolate mofetil IV 1 g twice a day or IVIG for 5 days or cyclophosphamide; taper corticosteroids over 4-6 weeks            Pulmonary and infectious disease consults if necessary            Bronchoscopy with BAL 6 transbronchial biopsy            Patients should be hospitalized for further management

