G3-4: Limiting self-care and aids warranted, weakness limiting walking, ANY dysphagia, facial weakness, respiratory muscle weakness, or rapidly progressive symptoms, or MGFA severity class 3-4 moderate to severe generalized weakness to myasthenic crisis	Permanently discontinue ICPi Admit patient, may need ICU-level monitoring Neurology consult Continue corticosteroids and initiate IVIG 2 g/kg IV over 5 days (0.4 g/kg/d) or plasmapheresis for 5 days Frequent pulmonary function assessment Daily neurologic review

Additional considerations            Avoid medications that can worsen myasthenia: b-blockers, IV magnesium, fluoroquinolones, aminoglycosides, and macrolides Initially a 5-day course of plasmapheresis or a 2 g/kg course of IVIG over 5 days            1-2 mg/kg methylprednisolone daily, wean based on symptom improvement            Pyridostigmine, wean based on improvement            ICPi-associated myasthenia gravis may be monophasic, and additional corticosteroid-sparing agents may not be required
	
7.2 Guillain-Barré syndrome	

Definition: Progressive, most often symmetrical muscle weakness with absent or reduced deep tendon reflexes. Often starts with sensory symptoms/neuropathic pain localized to lower back and thighs. May involve extremities
	

7.0 Nervous System Toxicities	
(typically ascending weakness but not always), facial, respiratory, and bulbar and oculomotor nerves. May have dysregulation of autonomic nerves.	
Diagnostic work-up Neurologic consultation MRI of spine with or without contrast (rule out compressive lesion and evaluate for nerve root enhancement/thickening) Lumbar puncture: CSF typically has elevated protein and often elevated WBCs; even though this is not typically seen in classic Guillain-Barré syndrome, cytology should be sent with any CSF sample from a patient with cancer. Serum antibody tests for Guillain-Barré syndrome variants (GQ1b for Miller Fisher variant a/w ataxia and ophthalmoplegia) Electrodiagnostic studies to evaluate polyneuropathy Pulmonary function testing (NIF/VC) Frequent neurochecks	
Grading	Management
All grades	Warrant work-up and intervention given potential for progressive Guillain-Barré syndrome to lead to respiratory compromise Note: There is no G1 toxicity
G1: Mild, none	NA
G2: Moderate, some interference with ADL, symptoms concerning to patient	Discontinue ICPI

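### Section 2.1.7 lets a Cohort 2 patient with an older, resolved severe immune event on a prior PD-1/PD-L1 inhibitor be re-exposed, and omits Table A10's uveitis exclusion

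*Combined protocol and SAP*

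**What the plan says.** **Eligibility.** Section 2.1.7.6 excludes active or recent autoimmune disease, with a few named exceptions, and a "recent history of a syndrome that required treatment with either systemic corticosteroids" above 10 mg daily prednisone equivalent or immunosuppressive drugs. The protocol gives no length of time for 'recent'.

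For Cohorts 2A and 2B, Sections 2.1.4 and 2.1.6 say "Patients must have been treated with at least one treatment of a PD-1/PD-L1 checkpoint inhibitor" for advanced or metastatic disease, and add a best-response category. Section 2.3.1 assigns cohorts by prior checkpoint therapy and "documented or reviewed radiologic responses to prior checkpoint inhibitor therapy". None of these asks about toxicity on the earlier drug or why it was stopped.

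**Stopping rules on study.** Section 3.3.1.2 states: "Any Grade 4 ADRs require permanent treatment discontinuation", with limited exceptions. Table 2 adds: "Permanent treatment discontinuation is required in case of immune-related Grade 4 rash/inflammatory dermatitis" and nine other named Grade 4 immune events. For Grade 3-4 pneumonitis, Table A3 in Appendix C says "Permanently discontinue ICPi". Section 3.3.1.8 softens its general Grade 4 advice "with the exception of endocrinopathies that have been controlled by hormone replacement".

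**Uveitis.** Under prior conditions, Table A10 tells the reader to exclude people who have had active uveitis, and lists recurrent uveitis that needed systemic immunosuppression or ongoing local treatment. Section 2.1.7 does not mention uveitis.

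**The concern.** M7824 contains an anti-PD-L1 antibody, so treating a Cohort 2 patient is re-exposure to the same drug class. The protocol judges some immune events serious enough to end that exposure for good when they arise on study. Its entry criteria do not apply the same judgement to an event that arose on an earlier inhibitor, provided the event is no longer recent.

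Two things are at stake. One is safety: Section 12.5.3 names the inclusion and exclusion criteria among the means of limiting risk to patients. The other is consistency: with 'recent' undefined, two investigators can reach opposite decisions on the same history, and a site working from 2.1.7 alone would not apply the uveitis exclusion in the appendix.

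**Working it through.** No arithmetic decides this point. The check sets the entry criteria beside the stopping rules.

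**1. Does any entry criterion bar an older, resolved immune event?**
- 2.1.7.6: active or recent only. Other criteria do state a window, such as 30 days for live vaccines (2.1.7.8) and two years disease-free for a second malignancy (2.1.7.7).
- 2.1.7.1: allergic reactions to similar compounds, with no time limit. Past class toxicity is thus a lasting bar for allergy but not for, say, pneumonitis.
- 2.1.7.2: uncontrolled current illness, not a resolved one.
- 2.1.7.11: bars prior PD-1/PD-L1 therapy in Cohorts 1A and 1B only.
- 2.1.1.10: laboratory limits detect residual organ dysfunction, not history.
- The remaining exclusions concern other matters, and 2.1.7 has no general investigator-judgement exclusion.

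The answer is no.

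**2. Can such a patient reach Cohort 2?** Yes. Section 2.3.1 describes the cohort as refractory, but 2.1.4 and 2.1.6 do not require progression while on the inhibitor. A patient who stopped for toxicity and progressed later satisfies the exposure, response and metastatic-disease criteria.

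**3. What would happen to the same event on study?**

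| Event | Source | Rule |
|---|---|---|
| Grade 4 drug reaction | 3.3.1.2 | Permanent stop, limited exceptions |
| Ten named Grade 4 immune events | Table 2 | Permanent stop |
| Grade 3-4 pneumonitis | Table A3 | Permanent stop |
| Guillain-Barré syndrome, Grade 2 | Table A7 | Discontinue |
| Myocarditis | Table A9 | Permanent stop after Grade 1, listed as an action to consider |

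Appendix C also urges caution about re-exposure after myositis and severe Guillain-Barré syndrome, and notes that toxicity has returned on rechallenge in polymyalgia-like syndrome.

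**4. Would screening bring the history to light?** Section 2.2.2 requires a complete medical history, and 6.1.1 records all prior immunotherapy. Neither specifically asks why the earlier inhibitor stopped or for the worst grade of any immune event on it.

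**5. Uveitis.** Section 2.1.7.6 would catch active or recent autoimmune uveitis, and a recent episode treated with systemic steroids or immunosuppressants. It would not catch an older history, or older recurrent uveitis managed with local treatment. Table A10 would exclude those patients.

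**6. Size of the cohort concerned.** From 10.2.3 and 10.2.4, Cohort 2A plans up to 16 evaluable patients and Cohort 2B up to 21: 16 + 21 = 37. The trial total is 15 + 16 + 16 + 21 = 68. The documents give neither the prevalence of such histories nor a recurrence rate, so 37 is not an estimate of patients affected.

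**The case against.** The best defence is that this is a deliberate choice. Re-treating checkpoint-exposed patients with limited options is the purpose of Cohort 2, and a remote, resolved event can be left to individual risk-benefit judgement. Screening runs under a separate protocol (01-C-0129) that is not available here, nor are the case report forms, and either may ask the missing questions. The research team also discusses each patient on active treatment weekly, and immune events are handled as events of special interest. Some of this stands: the statement about screening applies only to this protocol's text. But the protocol gives no rationale or conditions for re-exposure after an event that meets its stop rules, and monitoring after enrolment does not replace an entry criterion.

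A second defence is that Appendix C is generic class guidance. It advises on CTLA-4 agents not used here, and the table of contents omits it. That makes the uveitis mismatch partly editorial. Still, 3.3.1.8 gives organ-specific ASCO guidance precedence over its general rules. Reading the Appendix C tables as that guidance is an inference, but a natural one. The Grade 4 stops in 3.3.1.2 and Table 2 do not depend on it.

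Three stronger readings are tempting and are not supported:
- **That severe recent immune toxicity is admitted.** Section 2.1.7.6 already bars most of it, because these events are generally treated with systemic steroids or immunosuppressants.
- **That any event which ended the earlier inhibitor should bar entry.** Appendix C allows PD-1/PD-L1 agents to resume after Grade 2-3 colitis that recovers to Grade 1 or less, and after Grade 2 pneumonitis that does so. Such a bar would be stricter than the protocol's own rules.
- **That the gap can be sized by counting event types.** The count depends on what is included. Grade 4 venous thromboembolism carries a permanent stop in Table A9, for example, yet is treated with anticoagulants, and the table concedes that its cause may be impossible to establish.

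**Conclusion.** The gap is real on the text. Followed as written, the plan admits a Cohort 2 patient with an older, resolved immune event of a type and grade that would permanently end M7824 on study. Table A10 and 2.1.7 also disagree on past uveitis.

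The size is limited. Recent cases are largely covered, no patient count can be given, and the response-rate analysis, alpha and power are untouched. The conclusion assumes that 'recent' is read in its ordinary sense and that no document outside this protocol imposes the missing exclusion. Closing the gap is a cheap improvement to patient safety and consistent eligibility.

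**What to change.** Make three changes.

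(a) Add an exclusion for Cohorts 2A and 2B: any immune-related adverse event on a prior PD-1/PD-L1 inhibitor, regardless of when it occurred, of a type and grade requiring permanent discontinuation under Section 3.3.1.2, Table 2 or Appendix C, including myocarditis and Guillain-Barré syndrome. Exceptions: endocrinopathies controlled on hormone replacement, and venous thromboembolism not attributed to the inhibitor. Myocarditis and Guillain-Barré syndrome need naming because their stop wording is less firm. Lower-grade events that merely led to stopping the earlier drug should not be included.

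(b) Carry the Table A10 uveitis exclusion into 2.1.7 so that the two sections agree.

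(c) In 2.2.2, for Cohort 2, record why the prior inhibitor stopped and the type and worst grade of any immune event on it.

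Change (a) removes the dependence on 'recent' for the events that matter most. The word stays undefined for other histories, and the documents offer no basis for choosing a particular window.

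The cost is two eligibility lines and one screening item, plus a small loss of Cohort 2 candidates, who have limited alternatives. Accrual may slow slightly; the documents do not allow an estimate. No sample size or decision boundary changes.

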## 2.1.8 Recruitment Strategies

Both men and women and members of all races and ethnic groups are eligible for this trial. This protocol may be abstracted into a plain language announcement posted on NIH websites and on NIH social media. This study will be listed on [www.clinicaltrials.gov](http://www.clinicaltrials.gov) and participants will be recruited from the current patient population as well as referrals at NIH.

## 2.2 SCREENING EVALUATION

### 2.2.1 Screening activities performed prior to obtaining informed consent

Minimal risk activities that may be performed before the subject has signed a consent include the following:

- Email, written, in person or telephone communications with prospective subjects
- Review of existing medical records to include H&P, laboratory studies, etc.
- Review of existing MRI, x-ray, or CT images
- Review of existing photographs or videos
- Review of existing pathology specimens/reports from a specimen obtained for diagnostic purposes.

### 2.2.2 Screening activities performed after a consent for screening has been signed

Screening evaluation testing/procedures are conducted under the separate screening protocol, 01-C-0129 (Eligibility Screening and Tissue Procurement for the NIH Intramural Research Program Clinical Protocols). Assessments performed at outside facilities or on another NIH protocol within the timeframes below may also be used to determine eligibility once a patient has signed the consent.

All screening tests and procedures must be performed within 21 days prior to initiation of study therapy except physical exam with skin assessment, ECOG, vital signs, blood tests and pregnancy test (repeated if >7 days):

- Complete medical history and physical examination (including height, weight, vital signs, and ECOG performance status) and skin assessment.
- Electrocardiogram (ECG)
- CT scan of chest, abdomen and pelvis with IV and PO (as indicated) contrast, or CT chest and MRI abdomen/pelvis may be performed, and [18F]-Sodium Fluoride (NaF) PET/CT bone scan (if indicated).
- Laboratory assessments: CBC with differential, acute care panel (sodium, potassium, chloride, total CO2 (Bicarbonate), creatinine, glucose, urea nitrogen), mineral panel (albumin, calcium total, magnesium total, phosphorus), hepatic panel (alkaline phosphatase, ALT/GPT, AST/GOT, total bilirubin, direct bilirubin), ionized calcium, amylase, lipase, LDH, total protein, GGT, Hepatitis B and C, PT/INR, PTT, urine analysis.
- Hepatitis B and C antibody panel
- Thyroid function tests – TSH, reflex T3 and T4
- Pre-treatment tissue biopsy and/or archival tissue availability for PD-L1 expression retrospective testing is mandatory for enrollment. PD-L1 will be performed retrospectively by EMD Serono using a test determined by EMD Serono.
- Pregnancy test for females of childbearing-potential (within 3 days prior to first dose of study drug).
- Lymphocyte Phenotyping - CD4/CD8 will be performed on known HIV-positive patients.

